8.2.7. Concomitant Medication Review

Concomitant medications will be reviewed at each visit.

8.2.8. Injection-Site Reactions

An injection-site reaction is any adverse reaction at a SC study intervention injection site. Injection sites will be evaluated for reactions and any injection-site reaction will be recorded as an AE.

8.2.9. Hypersensitivity Reactions

Before any SC injection or IV infusion of study intervention, appropriately trained personnel and medications must be available to treat hypersensitivity reactions, including anaphylaxis. All participants must be observed carefully for signs and symptoms of a hypersensitivity reaction (eg, urticaria, pruritis, angioedema, wheezing, dyspnea, or hypotension).

In the case of anaphylaxis, injectable epinephrine (intramuscular), respiratory assistance, and other proper resuscitative measures are essential and must be available at the study site where the injections or infusions are being administered.

Participants who experience serious adverse reactions related to an injection or infusion must strongly be considered to be discontinued from further study intervention administrations.

Participants who experience reactions following an injection or infusion that result in bronchospasm with wheezing and/or dyspnea that requires ventilatory support, or symptomatic hypotension with a decrease in systolic blood pressure greater than 40 mm Hg or blood pressure <90/60 mm Hg must be discontinued from additional study intervention administration (see Section 7).

Participants who experience reactions suggestive of serum sickness (resulting in symptoms such as myalgia and/or arthralgia with fever and/or rash that are not representative of signs and symptoms of other recognized clinical syndromes) occurring 1 to 14 days after administration of study intervention, must be discontinued from further study intervention administration. Note that these signs and symptoms may be accompanied by other events including pruritus, facial, hand, or lip edema, dysphagia, urticaria, sore throat, and/or headache.

8.2.10. Adverse Events Temporally Associated With Infusion

Any AE (except laboratory abnormalities) that occurs during or within 1 hour after the IV infusion of study intervention will be carefully evaluated. Minor infusion-related AEs may be managed by slowing the rate of the IV infusion and/or treating with antihistamines and/or acetaminophen (paracetamol) as clinically indicated. If an IV infusion of study intervention is

interrupted because of an AE that, in the opinion of the investigator, is not severe or does not result in a serious adverse event (SAE), the infusion may be restarted with caution.

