7.1. Discontinuation of Study Intervention

A participant who discontinues study intervention will not be automatically withdrawn from the study (see Section 7.2).

A participant's study intervention must be discontinued under the following conditions:

1. The participant initiates treatment with prohibited concomitant medication(s) (Section 6.5.2).
2. The participant has a colectomy.
3. The participant becomes pregnant or plans a pregnancy within the study period. Refer to Appendix 4 (Section 10.4), Contraceptive and Barrier Guidance and Collection of Pregnancy Information.
4. The participant (or the participant's legally acceptable representative) withdraws consent for administration of study intervention.
5. The participant develops an opportunistic infection.

6. The participant is deemed ineligible according to the following TB screening criteria:
- A diagnosis of active TB is made.
 - A participant has symptoms suggestive of active TB based on follow-up assessment questions and/or physical examination, or has had recent close contact with a person with active TB, and cannot or will not continue to undergo additional evaluation.

A participant undergoing evaluation has a chest radiograph with evidence of current active TB and/or a positive or indeterminate QuantiFERON[®]-TB test result (and/or a positive tuberculin skin test result in countries in which the QuantiFERON[®]-TB test is not approved/registered or the tuberculin skin test is mandated by local health authorities).

Note: In Ukraine, while the QuantiFERON[®]-TB test is not approved/registered, it is accepted and a tuberculin skin test is not required.

7. Criterion modified per Amendment 2.

7.1. The participant has a serious adverse reaction that is related to an injection or an infusion, including an injection-site or infusion reaction, resulting in bronchospasm with wheezing and/or dyspnea that requires ventilatory support **OR** that results in symptomatic hypotension with a decrease in systolic blood pressure >40 mm Hg or blood pressure <90/60 mm Hg.

8. The participant has a reaction resulting in myalgia and/or arthralgia with fever and/or rash (suggestive of serum sickness and not representative of signs and symptoms of other recognized clinical syndromes) occurring 1 to 14 days after an injection of study intervention. These may be accompanied by other events including pruritus, facial, hand, or lip edema, dysphagia, urticaria, sore throat, and/or headache.

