3. The participant reports suicidal ideation with intention to act (“Ideation level 4”), suicidal ideation with specific plan and intent (“Ideation level 5”), or any suicidal behavior (actual suicide attempt, interrupted suicide attempt, aborted suicide attempt, or preparatory behaviors for making a suicide attempt) on a post-baseline C-SSRS assessment. If a participant can be adequately treated with psychotherapy and/or pharmacotherapy based on an evaluation by a mental health professional, then the participant, at the discretion of the investigator, may be continued with treatment if agreed to by the medical monitor or designee. Discussion of such participants with the medical monitor or designee is required (see Section 8.2.6).

4. Criterion deleted per Amendment 2.

5. The participant has hematology abnormalities as described below:

- Two sequential absolute neutrophil counts $<0.75 \times 10^3/\mu\text{L}$ (SI: $<0.75 \times 10^9/\text{L}$)
- Two sequential absolute lymphocyte counts $<0.5 \times 10^3/\mu\text{L}$ (SI: $<0.5 \times 10^9/\text{L}$)
- Two sequential hemoglobin values $<8.0 \text{ g/dL}$ (SI: $<80.0\text{g/L}$) or a decrease of $>30\%$ from baseline
- Two sequential platelet counts $<75 \times 10^3/\mu\text{L}$ (SI: $<75 \times 10^9/\text{L}$)

Note: These laboratory abnormalities should be discussed with the medical monitor or designee, and study intervention should be withheld until the clinical assessment is complete.

6. The participant develops a severe injection-site or infusion reaction.

If a participant discontinues study intervention for any reason before the end of the treatment period, assessments should be obtained as specified in the SoA (Section 1.3). If the reason for withdrawal from the study is withdrawal of consent, every effort should be made to conduct the early termination assessments, as indicated in the SoA, prior to terminating study participation. After termination of study participation, no additional assessments are allowed.

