8.2.3. Vital Signs

Temperature, pulse/heart rate, respiratory rate, and blood pressure will be assessed.

Blood pressure and pulse/heart rate measurements will be assessed with a completely automated device. Manual techniques will be used only if an automated device is not available.

If feasible, blood pressure and pulse/heart rate measurements should be preceded by at least 5 minutes of rest in a quiet setting without distractions (eg, television, cell phones).

At a study intervention administration visit, vital signs should be obtained before, approximately every 30 minutes during, and twice (at approximately 30-minute intervals) after completion of the IV infusion(s), or before and approximately 30 minutes after the SC injection, or if the participant reports any symptoms.

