Note: The sponsor collects adverse events starting with the signing of the ICF (refer to All Adverse Events under Section 8.3.1, Time Period and Frequency for Collecting Adverse Events and Serious Adverse Events Information, for time of last adverse event recording).

Serious Adverse Event

A serious adverse event based on ICH and EU Guidelines on Pharmacovigilance for Medicinal Products for Human Use is any untoward medical occurrence that at any dose:

- Results in death
- Is life-threatening
(The participant was at risk of death at the time of the event. It does not refer to an event that hypothetically might have caused death if it were more severe.)
- Requires inpatient hospitalization or prolongation of existing hospitalization
- Results in persistent or significant disability/incapacity
- Is a congenital anomaly/birth defect
- Is a suspected transmission of any infectious agent via a medicinal product
- Is Medically Important*

*Medical and scientific judgment should be exercised in deciding whether expedited reporting is also appropriate in other situations, such as important medical events that may not be immediately life-threatening or result in death or hospitalization but may jeopardize the participant or may require intervention to prevent one of the other outcomes listed in the definition above. These should usually be considered serious.

Unlisted (Unexpected) Adverse Event/Reference Safety Information

An adverse event is considered unlisted if the nature or severity is not consistent with the applicable product reference safety information. For guselkumab and golimumab, the expectedness of an adverse event will be determined by whether or not it is listed in the IB for guselkumab or for golimumab, respectively.

Adverse Event Associated With the Use of the Intervention

An adverse event is considered associated with the use of the intervention if the attribution is possible, probable, or very likely by the definitions listed below (see Attribution Definitions).

ATTRIBUTION DEFINITIONS

Not Related

An adverse event that is not related to the use of the intervention.

Doubtful

An adverse event for which an alternative explanation is more likely, eg, concomitant treatment(s), concomitant disease(s), or the relationship in time suggests that a causal relationship is unlikely.

Possible

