An adverse event that might be due to the use of the intervention. An alternative explanation, eg, concomitant treatment(s), concomitant disease(s), is inconclusive. The relationship in time is reasonable; therefore, the causal relationship cannot be excluded.

Probable

An adverse event that might be due to the use of the intervention. The relationship in time is suggestive (eg, confirmed by dechallenge). An alternative explanation is less likely, eg, concomitant treatment(s), concomitant disease(s).

Very Likely

An adverse event that is listed as a possible adverse reaction and cannot be reasonably explained by an alternative explanation, eg, concomitant treatment(s), concomitant disease(s). The relationship in time is very suggestive (eg, it is confirmed by dechallenge and rechallenge).

SEVERITY CRITERIA

An assessment of severity grade will be made using the following general categorical descriptors:

Mild: Awareness of symptoms that are easily tolerated, causing minimal discomfort and not interfering with everyday activities.

Moderate: Sufficient discomfort is present to cause interference with normal activity.

Severe: Extreme distress, causing significant impairment of functioning or incapacitation. Prevents normal everyday activities.

The investigator should use clinical judgment in assessing the severity of events not directly experienced by the participant (eg, laboratory abnormalities).

SPECIAL REPORTING SITUATIONS

Special reporting situations must be reported by the investigator or site staff personnel to the sponsor or designee within 24 hours after being made aware of the event. Safety events of interest on a sponsor study intervention in an interventional study that may require expedited reporting or safety evaluation include, but are not limited to:

- Overdose of a sponsor study intervention
- Suspected abuse/misuse of a sponsor study intervention
- Accidental or occupational exposure to a sponsor study intervention
- Any failure of expected pharmacologic action (ie, lack of effect) of a sponsor study intervention
- Unexpected therapeutic or clinical benefit from use of a sponsor study intervention
- Medication error involving a sponsor product (with or without participant/patient exposure to the sponsor study intervention, eg, name confusion)
- Exposure to a sponsor study intervention from breastfeeding

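### The infusion-restart rule in Protocol Section 8.2.10 joins its two conditions with 'or', so read literally it permits restart after a severe-only or a serious-only reaction

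*Protocol*

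**What the plan says.** Four parts of the protocol bear on this.

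- **Restart (Section 8.2.10).** The condition for resuming an infusion interrupted for an adverse event reads: "opinion of the investigator, is not severe or does not result in a serious adverse event (SAE), the infusion may be restarted with caution". The section does not refer to Section 7.1 or Section 8.2.9.
- **Discontinuation to be strongly considered.** Section 7.1, second list, item 6 covers severity: "The participant develops a severe injection-site or infusion reaction". Section 8.2.9 covers seriousness: "Participants who experience serious adverse reactions related to an injection or infusion must strongly be considered to be discontinued from further study intervention administrations".
- **Mandatory stop.** Section 8.2.9 names reactions with respiratory compromise needing ventilatory support and adds a blood-pressure trigger: "symptomatic hypotension with a decrease in systolic blood pressure greater than 40 mm Hg or blood pressure <90/60 mm Hg must be discontinued". What is stopped is any additional dosing. Section 7.1, first list, item 7.1 has the same clinical triggers and opens with: "The participant has a serious adverse reaction that is related to an injection or an infusion, including an injection-site or infusion reaction".
- **Definitions (Appendix 9).** Severity is graded by intensity: "Severe: Extreme distress, causing significant impairment of functioning or incapacitation". Seriousness is defined by outcome (death, threat to life, hospitalization and so on), with a medically-important category for events that "may require intervention to prevent one of the other outcomes listed in the definition above. These should usually be considered serious".

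**The concern.** A rule meant to allow restart only after reactions that are neither severe nor serious would negate the pair as a whole, or join the two negated conditions with 'and'. Section 8.2.10 does neither. Satisfying one condition is enough, so a severe reaction qualifies if it is not an SAE, and an SAE qualifies if it is not graded severe.

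Section 8.2.10 is the only place in the supplied documents that says when an interrupted infusion may be resumed, so site staff would look there. Every participant has an infusion, active or placebo, at Weeks 0, 4 and 8 (Section 6.1). What is at stake is a safety instruction applied at the bedside, not the analysis.

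**Working it through.** No figure in the plan needs to be reproduced. The check is a truth table followed by a comparison of sections.

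**Step 1. Put the rule into logical form.**

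- As written: restart permitted = (not severe) or (not serious) = not (severe and serious).
- With 'and': restart permitted = (not severe) and (not serious) = not (severe or serious).
- Discontinuation to be strongly considered (Section 7.1 item 6 for severe, Section 8.2.9 for serious) = severe or serious.

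**Step 2. Fill in the four combinations**, for reactions outside the mandatory stops.

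| Severe | Serious | 8.2.10 as written | 8.2.10 with 'and' | Elsewhere |
|---|---|---|---|---|
| No | No | may restart | may restart | no specific instruction |
| Yes | No | may restart | not permitted | strongly consider stopping (7.1 item 6) |
| No | Yes | may restart | not permitted | strongly consider stopping (8.2.9) |
| Yes | Yes | not permitted | not permitted | strongly consider stopping (both) |

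**Step 3. Count.** The wording permits restart in 3 of 4 combinations; with 'and' it is 1 of 4. In 2 of the 3, another section says that discontinuation must be strongly considered. With 'and' that overlap falls from 2 to 0. The combinations are not equally likely, so these counts describe the logic and not how often anything would happen.

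**Step 4. Are the two mixed rows possible?** Yes, because Appendix 9 defines the two terms on different scales. The medically-important clause makes the severe-but-not-serious row less common, since some severe reactions needing intervention will be classed as serious. It does not empty the row.

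**Step 5. Mandatory-stop reactions.** For these, Section 8.2.10 says 'may' and Sections 7.1 and 8.2.9 say 'must'. A permission gives way to a prohibition, and resuming an infusion is naturally a further administration. The stop therefore governs whatever Section 8.2.10 says.

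**Step 6. Scope.** Three infusions for each of 210 planned participants is 3 × 210 = 630 planned infusions to which the sentence could apply. This is an upper bound on exposure to the rule. The documents give no rate of interruption or of severe-only or serious-only reactions, so no count of affected infusions follows from it.

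**The case against.** The best defence is that nobody reads Section 8.2.10 alone. Section 8.2.9 comes immediately before it, investigators are bound by the whole protocol, and the preceding sentence in 8.2.10 concerns minor infusion-related events, which points to 'neither' as the intended meaning. Restart is optional, to be done with caution, and rests on the investigator's opinion. Section 7.1 first-list item 14 requires stopping whenever the investigator thinks that safety calls for it. Strongly considering discontinuation and then cautiously resuming are also compatible, so the two mixed rows are loose wording and not a contradiction. Finally, Section 6.1 sends sites to the IPPM and IPPI for detailed administration instructions. Those manuals were not supplied and may settle the matter.

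All of this stands as a limit on the harm. It does not change what the sentence says, and the intended meaning has to be supplied by the reader.

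A reader might go further and infer that Section 8.2.10 authorizes a restart that Sections 7.1 and 8.2.9 forbid, for example after symptomatic hypotension. The documents do not support that, for the reason in step 5. The same answer applies to Week 0, where the SC injections follow about 30 minutes after the infusion is complete: the mandatory stop already covers them. Section 8.2.9 states its stop without a seriousness threshold while Section 7.1 item 7.1 limits it to serious reactions, but that difference is a separate matter and not a fault of the restart rule.

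**Conclusion.** The sentence is wrong as written, and the error is minor. Taken literally, it leaves severe-only and serious-only reactions outside the mandatory stops eligible for restart, although the protocol elsewhere asks for discontinuation to be strongly considered after them. There is no true conflict with the mandatory stops.

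The conclusion rests on the ordinary meaning of 'or' between two separately negated conditions and on the separate definitions in Appendix 9. Its practical size cannot be given without an interruption rate, and it would shrink further if the site manuals state the restart rule correctly. The primary endpoint, power and alpha are not affected.

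**What to change.** In Section 8.2.10, replace 'or' with 'and' between the two conditions, so that restart requires an event that is not severe and also does not result in an SAE. End the sentence with: 'subject to the discontinuation criteria in Sections 7.1 and 8.2.9'.

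The 'and' is the substantive correction. The cross-reference is a clarification that puts the existing stops in view where the restart decision is made. Check that the IPPM and IPPI agree with the revised wording.

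The cost is one reworded sentence, by amendment or clarification letter. No visits, staff or procedures are added, and Section 8.2.3 already schedules vital signs about every 30 minutes during infusion.

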8.2.11. Infections

Study intervention should not be administered to a participant with a clinically significant, active infection. Investigators are required to evaluate participants for any signs or symptoms of infection at scheduled visits (see SoA, Section 1.3). If a participant develops a serious infection, including but not limited to sepsis or pneumonia, discontinuation of study intervention must be strongly considered.

8.2.12. Tuberculosis Evaluations

8.2.12.1. Initial Tuberculosis Evaluation

Participants must undergo testing for TB and their medical history assessment must include specific questions about a history of TB or known occupational or other personal exposure to individuals with active TB. The participant should be asked about past testing for TB, including chest radiograph results and responses to tuberculin skin or other TB testing. Investigators have the option to use both the QuantiFERON[®]-TB test and the tuberculin skin test (refer to Appendix 3 [Section 10.3]) to screen for latent TB if they believe, based on their judgment, that the use of both tests is clinically indicated in order to evaluate a participant who has high risk of having latent TB. If either the QuantiFERON[®]-TB test or the tuberculin skin test is positive, the participant is considered to have latent TB infection and is excluded from the study.

Participants with a negative QuantiFERON[®]-TB test result (and a negative tuberculin skin test result in countries in which the QuantiFERON[®]-TB test is not approved/registered or the tuberculin skin is mandated by local health authorities) are eligible to continue with pre-randomization procedures. Participants with a newly identified positive QuantiFERON[®]-TB (or tuberculin skin) test result are excluded from the study and must undergo an evaluation to rule out active TB and initiate appropriate treatment for latent TB. Appropriate treatment for latent TB is defined according to local country guidelines for immunocompromised patients. If no local country guidelines for immunocompromised patients exist, US guidelines must be followed. For a participant with an indeterminate QuantiFERON[®]-TB test, the test may be repeated once. If the result is indeterminate on repeat testing, the participant is considered a screen failure.

8.2.12.2. Ongoing Tuberculosis Evaluation

Early Detection of Active Tuberculosis

To aid in the early detection of TB reactivation or new TB infection during study participation, participants must be evaluated for signs and symptoms of active TB at scheduled visits (refer to the SoA in Section 1.3) or by telephone contact approximately every 8 to 12 weeks. The following series of questions is suggested for use during the evaluation:

- “Have you had a new cough of >14 days’ duration or a change in a chronic cough?”
- “Have you had any of the following symptoms:

- Persistent fever?
- Unintentional weight loss?
- Night sweats?”
- “Have you had close contact with an individual with active TB?” (If there is uncertainty as to whether a contact should be considered “close,” a physician specializing in TB should be consulted.)

If the evaluation raises suspicion that a participant may have TB reactivation or new TB infection, an immediate and thorough investigation should be undertaken, including, where possible, consultation with a physician specializing in TB.

Investigators should be aware that TB reactivation in immunocompromised participants may present as disseminated disease or with extrapulmonary features. Participants with evidence of active TB should be referred for appropriate treatment.

Participants who experience close contact with an individual with active TB during the conduct of the study must have a repeat chest radiograph, a repeat QuantiFERON[®]-TB test, a repeat tuberculin skin test in countries in which the QuantiFERON[®]-TB test is not approved/registered or the tuberculin skin test is mandated by local health authorities, and, if possible, referral to a physician specializing in TB to determine the participant’s risk of developing active TB and whether treatment is warranted. Study intervention administration should be interrupted during the investigation. A positive QuantiFERON[®]-TB test or tuberculin skin test result should be considered detection of latent TB. Participants with a positive or indeterminate QuantiFERON[®]-TB test or positive tuberculin skin test must immediately discontinue further administration of study intervention and be encouraged to return for scheduled study visits according to the SoA (Section 1.3).

